20.2. Independent Medical Reviewer

A single Independent Medical Reviewer (IMR) with pertinent expertise, will review and adjudicate relevant events reported by study investigators only for subjects who have received Tria™ Firm or Tria™ Soft stents. The IMR will also review and adjudicate all imaging and deaths reported by study investigators, regardless of stent type. The IMR will review a safety event dossier, which may include copies of subject source documents provided by study sites.

IMR responsibilities, qualifications, membership, and procedures are outlined in the IMR Charter.

20.3. Steering Committee

A Steering committee composed of recognized key opinion leaders/physicians in the field of Urology will be convened. The Steering Committee for the study will provide the following:

- Oversight of protocol development, data integrity, and timely dissemination and publication of the study results, and
- Prepare for, participate in, and/or facilitate investigator meetings, study Steering committee meetings or any other meetings at BSC's request, providing, among other things, leadership, protocol insight, and
- Serve as a general spokesperson for the study through word of mouth and podium presence at major clinical conferences, symposia, and various educational meetings, and

- Prepare for, participate in, and/or facilitate scheduled teleconferences, webcasts, and one-on-one contact with site investigators to discuss enrolment issues, study progress, and/or any new or pertinent study information, and
- Advise and assist BSC with the data preparation and analysis process.

21. Suspension or Termination

21.1 *Premature Termination of the Study*

Boston Scientific reserves the right to terminate the study at any stage but intends to exercise this right only for valid scientific or business reasons and reasons related to protection of subjects. Investigators, associated IRBs/ECs/REBs, and regulatory authorities, as applicable, will be notified in writing in the event of study termination.

21.1.1 **Criteria for Premature Termination of the Study**

Possible reasons for premature study termination include, but are not limited to, the following:

- Suspicion of an unacceptable risk, including serious health threat. In this case, the sponsor shall suspend the clinical investigation while the risk is assessed. The sponsor shall terminate the clinical investigation if an unacceptable risk which cannot be controlled is confirmed.
- Instructions by the IRB/EC/REB or regulatory authorities to suspend or terminate the clinical investigation.
- An enrollment rate far below expectation that prejudices the conclusion of the study.
- A decision on the part of Boston Scientific to suspend or discontinue development/marketing of the device.

21.2 *Termination of Study Participation by the Investigator or Withdrawal of IRB/EC/REB Approval*

Any investigator, or associated IRB/EC/REB or regulatory authority may discontinue participation in the study or withdraw approval of the study, respectively, with suitable written notice to Boston Scientific. Investigators, associated IRBs/ECs/REBs, and regulatory authorities, as applicable, will be notified in writing in the event of these occurrences.

21.3 *Requirements for Documentation and Subject Follow-up*

In the event of premature study termination, a written statement as to why the premature termination has occurred will be provided to all participating sites by Boston Scientific. The IRB/EC/REB and regulatory authorities, as applicable, will be notified. Detailed information on how enrolled subjects will be managed thereafter will be provided.

In the event an IRB/EC/REB terminates participation in the study, participating investigators, associated IRBs/ECs/REBs, and regulatory authorities, as applicable, will be notified in writing. Detailed information on how enrolled subjects will be managed thereafter will be provided by Boston Scientific.

In the event a Principal Investigator terminates participation in the study, study responsibility will be transferred to another investigator, if possible. In the event there are no opportunities to transfer Principal Investigator responsibility; detailed information on how enrolled subjects will be managed thereafter will be provided by Boston Scientific.

The Principal Investigator or his/her designee must return all study-related documents and devices, if supplied by Boston Scientific, unless this action would jeopardize the rights, safety, or welfare of the subjects.

21.4 Criteria for Suspending/Terminating a Study Site

Boston Scientific reserves the right to stop the inclusion of subjects at a study site at any time after the study initiation visit if no subjects have been enrolled for a period beyond 3 months after site initiation, or if the site has multiple or severe protocol violations/noncompliance without justification and/or fails to follow remedial actions.

In the event of termination of site participation, all devices and testing equipment, as applicable, will be returned to BSC unless this action would jeopardize the rights, safety or well-being of the subjects. The IRB/EC/REB and regulatory authorities, as applicable, will be notified. Study participants will be contacted, as applicable, and be informed of changes to study visit schedule.

22. Study Registration and Results

22.1. Study Registration

To comply with applicable laws and regulations, the study will be registered on a publicly accessible database.

22.2. Clinical Investigation Report

Study results will be made available in accordance with the legal requirements and the recognized ethical principles, in accordance with the Boston Scientific Policy. A Clinical Investigation Report will be made available to all investigators, IRB/EC/REB and regulatory authorities, as applicable in accordance with the Boston Scientific Policy and local requirements. As applicable an abbreviated Clinical Investigation Report will be made available on a publicly accessible database.

23. Publication Policy

BSC requires disclosure of its involvement as a sponsor or financial supporter in any publication or presentation relating to a BSC study or its results. BSC will submit study results for publication (regardless of study outcome) following the conclusion or termination of the study. Boston Scientific adheres to the Contributorship Criteria set forth in the Uniform Requirements of the International Committee of Medical Journal Editors (ICMJE; <http://www.icmje.org>). In order to ensure the public disclosure of study results in a timely manner, while maintaining an unbiased presentation of study outcomes, BSC personnel may assist authors and investigators in publication preparation provided the following guidelines are followed:

- All authorship and contributorship requirements as described above must be followed.
- BSC involvement in the publication preparation and the BSC Publication Policy should be discussed with the Coordinating Principal Investigator(s) and/or Executive/Steering Committee at the onset of the project.
- The First and Senior authors are the primary drivers of decisions regarding publication content, review, approval, and submission.

The data, analytic methods, and study materials for this clinical trial may be made available to other researchers in accordance with the Boston Scientific Data Sharing Policy (<https://www.bostonscientific.com/>).

24. Reimbursement and Compensation for Subjects

24.1. *Subject Reimbursement*

Subjects may be compensated for participation in the study, in accordance with pertinent country laws and regulations and per the study site's regulations.

24.2. *Compensation for Subject's Health Injury*

Boston Scientific will purchase an insurance policy to cover the cost of potential health injury for study subjects, if required by applicable law.

25. Bibliography

26.1. Abbreviations

Abbreviations are shown in Table 26.1.

Table 26.1: Abbreviations	
Abbreviation/Acronym	Term
AE	Adverse Event
AT	As Treated
BSC	Boston Scientific Corporation
CA	Competent Authority
CCGs	Case Report Form Completion Guidelines
DFU	Directions for Use
EC	Ethics Committee
eCRF	Electronic Case Report Form
EDC	Electronic Data Capture
GDPR	Global Data Protection
HIPAA	Health Information Portability and Accountability Act
ICF	Informed Consent Form
IFU	Instructions For Use
IRB	Institutional Review Board
ITT	Intent to Treat
PP	Per Protocol
QoL	Quality of Life
REB	Research Ethics Board
SAE	Serious Adverse Event
SADE	Serious Adverse Device Effect
SOC	Standard of Care
UAS	Ureteral Access Sheaths
UDS	Urinary Diversion Stent
US	Ureteral Stent

26.2. Definitions

Terms are defined in Table 26.2.

Table 26.2: Definitions

Term	Definition
Adverse Device Effect	See Table 18.2-1, Safety Definitions
Adverse Event	See Table 18.2-1, Safety Definitions
As Treated	All subjects for whom placement of the device is completed.
Consent Ineligible	A subject who has signed the ICF but is found to not meet eligibility criteria. These subjects can still receive the BSC Ureteral Stent per standard of care treatment, but do not count toward enrollment. The subjects will be exited and will not undergo any study related procedures once their ineligibility has been determined. These subjects do not count toward enrollment.
Data Controller	In GDPR: The entity which determines the purposes (why the entity needs to process data) and means (database managed through a software, hard copy files, centralized database) of personal information processing.
Data Processor	In GDPR: The person or entity processing the data on behalf and according to the instructions of the data controller. An entity which uses an external data processor must ensure that, in the contract, its data processor offers adequate guarantees to ensure the security and confidentiality of the data communicated.
Data Subject	In GDPR: Any living individual to whom the personal data relates. Examples of data subjects in this study are physicians and subjects.
Deviation (Clinical Protocol)	A departure from the requirements established in the clinical trial protocol (e.g., inclusion/exclusion criteria; visit windows, required procedures, and any specified consenting process requirements).
Exited Prior to Procedure	A subject who signs the informed consent, meets eligibility criteria but then does not undergo have the index study procedure initiated (first incision) or receive the study device. The original ICF and screening documentation for these patients should be maintained in the site's files. There are no follow-up requirements and these subjects do not count toward enrollment. Any data collected prior to procedure is not included in statistical analyses. These subjects do not count toward enrollment.
General Data Protection Regulation (GDPR)	The General Data Protection Regulation (GDPR) is a European law that will govern how companies (whether EU-based or not) use personal data.
Identifiers	“Identifiers” are personal data that can be used alone or in combination with other identifiers to identify an individual.
Index Procedure	Describes the entirety of the procedure in which the stent is implanted; includes ureteral access sheath insertion, scoping, irrigation, laser lithotripsy, basketing, stent implant, etc.
Independent Medical Reviewer	An independent practitioner with trial relevant therapeutic expertise that reviews and adjudicates important endpoints and relevant adverse events reported by study investigators.
Intent-To-Treat	A subject who signs the informed consent, meets eligibility criteria, and for whom the index procedure is initiated.
Minimal Risk	The probability and magnitude of harm or discomfort anticipated in the research are not greater in and of themselves than those ordinarily encountered in daily life or during the performance of routine physical or psychological examinations or tests.

Table 26.2: Definitions

Term	Definition
Monitoring	
EN ISO 14155Act of overseeing the progress of a clinical investigation and to ensure that it is conducted, recorded, and reported in accordance with the CIP, written procedures, this International Standard, and the applicable regulatory requirements
 
ICH E6 1.38 - The act of overseeing the progress of a clinical study and of ensuring that it is conducted, recorded, and reported in accordance with the protocol, Standard Operating Procedures (SOPs), GCP, and the applicable regulatory requirement(s).
 
FDA Guidance - Generally refers to the methods used by sponsors of investigational studies, or CROs delegated responsibilities for the conduct of such studies, to oversee the conduct of and reporting of data from clinical investigations, including appropriate investigator supervision of study site staff and third-party contractors.

Multi-center study	A clinical trial conducted according to a single protocol but at more than one site, and therefore carried out by more than one investigator.
Patient-Reported Outcome (PRO)	A measurement based on a report that comes directly from the patient (i.e., study subject) about the status of a patient's health condition without amendment or interpretation of the patient's response by a clinician or anyone else. A PRO can be measured by self-report or by interview provided that the interviewer records only the patient's response.
Per Protocol	All subjects in the As Treated Population who have no major protocol deviations.
Personal Data	GDPR defines “Personal data” to be any information relating to an identified or identifiable natural person (‘data subject’); an identifiable natural person is one who can be identified, directly or indirectly, in particular by reference to an identifier such as a name, an identification number, location data, an online identifier or to one or more factors specific to the physical, physiological, genetic, mental, economic, cultural or social identity of that natural person.
Point of Enrollment	Time at which subject has signs and dates the informed consent (ICF) and meets the eligibility criteria.
Processing	Any use of personal data by BSC (or a third party on behalf of BSC), including data collection, data sharing, anonymization, and data storage (note the mere storage of data is considered as processing).
RAVE	Proprietary electronic data capture system for capturing, managing and reporting clinical study data.
Recruitment	Active efforts to identify subjects who may be suitable for enrollment in the clinical investigation.
Sensitive Personal Data	GDPR defines “Sensitive personal” data as a subset of Personal Data, which, due to their nature have been classified as deserving additional privacy and security protections because their processing may create a risk for an individual’s fundamental right and freedom.
Serious Adverse Device Effect (SADE)	See Table 18.2-1, Safety Definitions

Table 26.2: Definitions

Term	Definition
Serious Adverse Event (SAE)	See Table 18.2-1, Safety Definitions
Site Noncompliance	A departure from the regulations established by the relevant regulatory authorities. Includes all clinical site noncompliance that does not represent a direct deviation from the clinical trial protocol, e.g. IRB/IEC and sponsor reporting, device storage and accountability, staff qualifications and training, facilities, and equipment required to conduct the clinical trial, collection and documentation of data in source documents and CRFs, investigator oversight, etc.
Source Data	All information in original records of clinical findings, observations, or other activities in a clinical investigation, necessary for the reconstruction and evaluation of the clinical investigation. (Ref. ISO 14155-2011)
Source Document	Printed, optical or electronic document containing source data. Examples: Hospital records, laboratory notes, device accountability records, photographic negatives, radiographs, records kept at the investigation site, at the laboratories and at the medico-technical departments involved in the clinical investigation. (Ref. ISO 14155-2011)
Study Stent Implant Procedure	Describes the portion of the index procedure only inclusive of placing the stent
Technical Success	For Ureteral Stents: Stented kidney drains (to bladder) during the planned indwell time with no re-intervention due to obstruction of the stented ureters For Urinary Diversion Stents: Drainage following stent placement during the planned indwell time with no re-intervention due to obstruction

27. Appendices

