Indication(s) for Use	
Boston Scientific Ureteral Stents are indicated for use to facilitate drainage from the kidney to the bladder, via endoscopic or fluoroscopic placement by a trained physician
 
Boston Scientific Urinary Diversion Stents are indicated for drainage following percutaneous, endoscopic, or operative procedures

Device/System applied as Standard of Care	
Boston Scientific Ureteral Stents, including (but not limited to):
 
• Contour™ Ureteral Stent• Contour VL™ Ureteral Stent• Contour™ Injection Ureteral Stent• Contour VL™ Injection Ureteral Stent• Percuflex™ Ureteral Stent• Percuflex™ Plus Ureteral Stent• Percuflex™ Urinary Diversion Stent (UDS)• Polaris™ Ultra Ureteral Stent• Polaris™ Loop Ureteral Stent• Tria™ Soft Ureteral Stent• Tria™ Firm Ureteral Stent• Contour™ SureDrive™ Steerable Ureteral Stent Set• Contour VL™ SureDrive™ Steerable Ureteral Stent Set• Percuflex™ Plus SureDrive™ Steerable Ureteral Stent Set
Study Design	A prospective multi-center global registry

Boston Scientific Double-J PLUS Ureteral Stent Postmarket Patient Registry DJUS PLUS Registry	
	<pre> graph TD A([Informed Consent and Eligibility Informed consent form and HIPAA Authorization signed by patient Eligibility check]) --> B{Subject meets enrollment criteria Signed ICF and met eligibility criteria} B -- No --> C([Screen Failure No further study activities]) B -- Yes --> D[Baseline Assessments Demographics, Medical History, Lab tests - Blood test and Urinalysis, QOL questionnaires] D --> E{Index Procedure Ureteral Stent Implant, Stent Performance, Medications, AE Assessment} E -- No --> F([Stent Placement not successful No further study activities]) E -- Yes --> G{Planned indwell greater than 90 days} G -- Yes (Long-term ≥90 days indwell) --> H[Post-Procedure Follow-up (≤ 90 days from Index procedure) Stent Performance and AE Assessment] G -- No (Short-term ≤ 90 days indwell) --> I[Stent Removal Visit (up to maximum indwell time as indicated in individual stent DFU/IFU) Stent Performance, Stent explant, QoL questionnaire and AE assessment] I --> J[Post-Stent Removal Visit (3-12 weeks from Stent Removal Visit) AE Assessment, QoL questionnaire Lab tests - Serum Creatinine and GFR (if SOC)] J --> K{Is a new stent placed?} K -- Yes --> L([End of Study]) K -- No --> J </pre>
Planned Number of Subjects	Up to 1,000 subjects in the Registry. Target enrollment of 25 subjects per stent type, unless otherwise noted

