Under normal conditions, urine is carried from the kidneys to the bladder via the ureters. A ureter may become obstructed as a result of a number of conditions including kidney stones, tumors, blood clots, postsurgical swelling, or infection. When the urine flow is blocked, it backs up into the kidney, which can lead to kidney swelling or hydronephrosis, as well as severe pain in the abdomen, flank, or side; nausea; vomiting; and hematuria. The goal of treatment for ureteral obstruction is to relieve or reduce the blockage and restore urinary drainage. Ureteral obstruction is commonly treated via placement of a ureteral stent; a thin, flexible tube that is threaded into the ureter and restores the flow of urine to the bladder. The most common reason for urinary diversion is bladder cancer that requires the bladder to be removed, a procedure called a cystectomy. Urinary diversion creates a new way for urine to exit body when urine flow is blocked or when there is a need to bypass the urinary tract.

The patient is usually placed under anesthesia for stent insertion, ensuring that the patient remains relaxed and immobile during the procedure. A cystoscope is inserted into the urethra to the bladder, and the opening to the ureter is identified. In some instances, a guidewire is inserted into the ureter under the aid of a fluoroscope. The stent is loaded onto the guidewire and subsequently advanced over the guidewire by a stent positioner (pusher). Once the stent is in place, the guidewire, positioner, and cystoscope are removed. If retrograde stenting is not possible, patients may have the stent placed percutaneously into the kidney, and subsequently into the ureter. Postoperative urine flow is monitored to ensure the stent has not been dislodged or obstructed. The stent may remain in place on a short-term (days to weeks) or long-term (weeks to months) basis and is removed most often cystoscopically. A

stent may also be removed with the attached retrieval line by a physician or nurse in an office setting or by the patient at home.

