9.2.2. Involuntary Withdrawal

Subjects may be involuntarily withdrawn from the study if the Investigator determines it is in the subject's best interest. If the subject is withdrawn at the investigator's discretion, the reason for withdrawal must be documented in the subject's medical records. Subjects who did not receive the study stent (implant failures) will be followed through hospital discharge and will be considered withdrawn.

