10.6. Index Procedure –BSC Ureteral Stent Placement

Index procedure is defined as the start time of sedation and/or anesthesia and includes the entirety of the procedure in which the study stent is implanted, however also includes ureteral access sheath insertion, scoping, irrigation, laser lithotripsy, basketing, etc. The stent placement will be performed by a trained physician and per the individual stent IFU/DFU.

Note: Baseline visit information may be collected on same day, prior to the index procedure.

After the index procedure, the following data will be collected:

- Stent Information – type, size, stent laterality (left or right), unilateral or bilateral, time of stent placement
- Stent Performance Assessment – implanted and performed as indicated within IFU/DFU
- Accessory Device Performance and Safety Assessment (BSC Guidewire, BSC Ureteral Access Sheaths {UAS}, BSC Stent Positioner, BSC UDS Accessories) - used during the index procedure
- Medication Assessment (post-procedure) - antibiotics, NSAIDs, anticholinergic, narcotic/opioid, Diuretic, Phenazopyridine, Alpha blockers
- Assessment of Adverse Events (including Clavien-Dindo Classification) and Device Deficiencies (including stent migrations and stent dislodgements)

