11.2. General Statistical Methods

11.2.1. Analysis Sets

The Intent-to-Treat (ITT) subject population includes all subjects who provide written informed consent to be enrolled into the study, and have the stent placement procedure initiated.

The As Treated (AT) Population includes all subjects for whom the stent placement is completed.

The Per Protocol (PP) population includes all subjects in the AT Population who meet all eligibility criteria.

The endpoint analyses will be performed for the ITT population. The AT and PP populations will be evaluated as sensitivity analyses for the primary efficacy endpoint and the safety outcomes will also be assessed using the AT population.

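### Table 26.2 dates the start of the procedure from first incision, so a failed cystoscopic placement literally meets a no-follow-up status that sections 10.6, 9.2.2/9.4 and both ITT definitions contradict

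*Combined protocol and SAP*

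**What the plan says.** Table 26.2 applies the status Exited Prior to Procedure to a consented, eligible subject who "does not undergo have the index study procedure initiated (first incision) or receive the study device". The consequences follow in the same entry: "There are no follow-up requirements and these subjects do not count toward enrollment", and "Any data collected prior to procedure is not included in statistical analyses".

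Other parts of the protocol treat the start of the procedure, and the subject who cannot be stented, differently:

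- Section 10.6: "Index procedure is defined as the start time of sedation and/or anesthesia".
- Section 9.2.2: "Subjects who did not receive the study stent (implant failures) will be followed through hospital discharge and will be considered withdrawn". Section 9.4 says the same in substance.
- Section 11.2.1 defines ITT as "all subjects who provide written informed consent to be enrolled into the study, and have the stent placement procedure initiated". The ITT entry in Table 26.2 requires consent, eligibility and an initiated index procedure. Neither mentions an incision.
- The Index Procedure entry in Table 26.2 covers the whole procedure and lists scoping and access sheath insertion among its parts.
- The study design chart in the synopsis ends the unsuccessful-placement branch with "Stent Placement not successful No further study activities".

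Section 4.2 describes the usual route: "A cystoscope is inserted into the urethra to the bladder, and the opening to the ureter is identified". A percutaneous route is mentioned for when retrograde stenting is not possible.

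**The concern.** The test that decides whether a subject left before the procedure is an event that the usual procedure does not contain. A subject who has been anaesthetised and instrumented, and whose placement then fails, fits a status meant for people who never reached the procedure.

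What is at stake is consistent disposition and event capture. Section 18.1 makes events reportable from the index procedure onward, and section 10.6 collects adverse events, device deficiencies and accessory performance after it. A site working from Table 26.2 or from the chart could close the subject's record at once. A site working from 9.2.2 would follow the subject to discharge. With up to 35 sites, failed attempts could be recorded in different ways.

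**Working it through.** **The plan's own figure first.** The only computed figure that could be affected is the Tria stone-management sample size in section 11.1.1.2. Inputs from that section and 11.1.1.3: goal 0.85, expected rate 0.94, one-sided alpha 0.025, power 0.90, attrition 10%, and success if the two-sided 95% Clopper-Pearson lower bound exceeds 0.85.

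- At n = 127, the smallest count whose lower bound exceeds 0.85 is 116.
- Exact alpha = P(X ≥ 116 | n = 127, p = 0.85) = 0.0245.
- Exact power = P(X ≥ 116 | n = 127, p = 0.94) = 0.920. At n = 126 the power is 0.864.
- Attrition: 127 / (1 − 0.10) = 141.1, rounded up to 142.

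Both figures reproduce. Section 11.1.1.3 analyses only stents in place for at least 12 hours, so a subject who never received a stent is outside this calculation under any definition of the start. Nothing here changes.

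**The rest is a comparison of passages.** Take a consented, eligible subject who is anaesthetised and scoped through the urethra, but whose stent cannot be placed.

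| Passage | Test | Result |
|---|---|---|
| Table 26.2, Exited Prior to Procedure | No incision, no device | Status met: no follow-up, not counted |
| Section 10.6 | Sedation or anesthesia started | Index procedure has begun |
| Sections 9.2.2, 9.4 | Study stent not received | Followed through discharge, then withdrawn |
| Section 11.2.1, ITT | Stent placement procedure initiated | In ITT if placement was attempted |
| Table 26.2, ITT | Index procedure initiated | In ITT |
| Synopsis chart | Placement not successful | No further activities |

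The conjunction in the Table 26.2 entry can mean that both conditions are absent, or that the absence of either is enough. This subject has neither an incision nor a device, so the status is met on both readings.

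**Percutaneous and operative cases.** Here an incision may exist. The conflict then narrows to subjects stopped between anesthesia and incision: 10.6 says the procedure began, and Table 26.2 says it did not.

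**The triggers differ in a further way.** Section 11.2.1 refers to the stent placement procedure, while Table 26.2 defines the study stent implant procedure as only the part of the index procedure in which the stent is placed. A subject who is sedated but stopped before that part has started the index procedure under 10.6, yet may be outside ITT under 11.2.1. If only the incision wording were replaced by the 10.6 start point, this subject would be neither exited nor clearly in ITT.

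**Reporting.** Section 11.1.2.2 summarises SADEs and adverse events for each stent type implanted. A subject with no implanted stent has no assigned row, even when in ITT.

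**The case against.** The strongest reply is that this is one parenthesis in one glossary row. The row's title, its reference to screening documentation, and its exclusion of only pre-procedure data all point to subjects who never reached the procedure. Sections 9.2.2 and 9.4 deal with implant failures specifically, and none of the operative sections uses an incision test. That is a fair account of the intent, and it limits the point to a conflict of wording. It does not remove the conflict: the row states a disposition rule, and a failed cystoscopic placement satisfies it as written.

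The reply also disposes of several stronger readings that a reader might infer:

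- *That Table 26.2 takes these subjects out of ITT.* The documents do not support this. The table's own ITT entry has no incision test, and its Index Procedure entry includes scoping.
- *That event capture ends.* Section 18.1, Table 10.1 and section 10.6 still require assessment and reporting at the index procedure. An absence of follow-up requirements does not cancel them.
- *That a per-type event rate shifts by a known amount.* One might set 1/26 (3.8%) against 0/25 for a stent type with 25 implanted subjects and one failed attempt with an event. That count is assumed, and the 1/26 is not clearly what the plan would report, because section 11.1.2.2 tabulates by stent type implanted.

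The chart is weaker evidence than the text. Its box can be read as meaning no further study visits, which is compatible with follow-up to discharge. It should still be worded so that only one reading is possible.

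**Conclusion.** The conflict is real and limited. As written, a subject anaesthetised and scoped but not stented is exited without follow-up under Table 26.2, has started the index procedure under 10.6, is followed to discharge under 9.2.2/9.4, and belongs to ITT once placement has been initiated. The consequence is that disposition and in-hospital event capture for failed placements can differ between sites.

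The powered Tria test and the 127/142 sample size are unaffected. The size of the effect on safety counts cannot be computed, because the documents give no placement-failure rate. That failed attempts would be under-recorded rests on the assumption that some sites apply Table 26.2 or the chart literally. The point deserves correction because the repair is cheap and the non-Tria groups are small: where the minimum target is 15 per type, one attempt recorded or not can matter to a summary.

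**What to change.** Reconcile the passages on a single initiation event:

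1. In Table 26.2, replace the incision wording under Exited Prior to Procedure with the section 10.6 start point.
2. Use the same trigger in the ITT definitions in section 11.2.1 and Table 26.2, so that a subject sedated but stopped before stent placement does not fall between categories.
3. Reword the unsuccessful-placement box in the synopsis chart to agree with sections 9.2.2 and 9.4, and check Figure 7.1 for the same box.
4. In section 11.1.2.2, state that ITT subjects with a failed placement are included in the safety summaries, either under the intended stent type or in a separate row for attempted but not implanted.

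The cost is wording only, with no change to sample size. The downside is a few more ITT subjects with in-hospital data only, and a slightly less favourable count of procedure-related events.
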